### 152 **3.1. Proportion of Participants with Progression $\geq 0.5D$ , $1D$ , and $2D$**

153 The proportion of participants with progression  $\geq 0.5D$ ,  $\geq 1D$ , and  $\geq 2D$  from baseline  
154 to 12, 24, and 30 months in each treatment group will be tabulated. The proportions will  
155 be compared between treatment groups using Barnard's test.  
156  
157

158

159

160 **3.2.Change in Axial Length at 12 and 24 Months (On Treatment)**

161 Axial length will be reported as the distributions of baseline length, 12-month length, 24-  
162 month length, and change in axial length from baseline to 12 and 24 months. A treatment  
163 group comparison of the change in axial length from baseline to 12 months and 24  
164 months will be performed using a longitudinal discrete time mixed model with maximum  
165 likelihood estimation, which allows for interaction between time and treatment group,  
166 and adjusts for the same baseline covariates as the primary analysis. The same strategies  
167 specified in the primary analysis (Section 1, excluding sensitivity analysis) will be used  
168 to choose the appropriate covariance structure for the model.

169

170 At baseline and all follow-up visits, including the 12 and 24-month visits, the mean of the  
171 axial length readings in both eyes for each participant will be used for the analysis. If data  
172 from only one eye is available, the reading on that eye will be used for analysis. The  
173 treatment group differences (atropine – placebo) and a 95% confidence interval will be  
174 estimated using the mixed model.

175

176 **3.3.Change in Axial Length at 30 Months (Off Treatment)**

177 The same approach defined in Section 3.4 will be used to conduct a treatment group  
178 comparison of the change in axial length from baseline to 30 months.

179

180 **3.4.Refractive Error at 12 Months (On Treatment)**

181 The primary analysis specified in Section 1 (excluding the sensitivity analysis) will be  
182 used to obtain a treatment group comparison of change from baseline to 12-months in  
183 SER, as measured by a masked examiner using cycloplegic autorefraction.

184

185 **3.5.Near Accommodation at 6 Months**

186 As a post hoc analysis, mean binocular near point of accommodation at 6 months will be  
187 compared between treatment groups using an ANCOVA model, adjusting for baseline  
188 binocular near point of accommodation, age, iris color (brown vs. not brown), and race  
189 (East Asian vs. non-East Asian).

190

191

192 **4. Subgroup Analysis**

193 The treatment group difference for change in SER from baseline to 24 and 30 months  
194 within the following subgroups will be explored:

195

- East Asian vs. non-East Asian race

196

- Brown iris versus non-brown iris

197

- Baseline younger versus older age (based on median split)

198

- Baseline lower versus higher myopia level by SER (based on median split)

199

- Baseline age and baseline SER (4 categories based on median splits)

200

201 An estimate of the treatment effect within each subgroup and a 95% confidence interval  
202 will be obtained for each of the times, 24 and 30 months, by adding a treatment by time

203 by subgroup interaction into the primary analysis model and generating the appropriate  
204 contrasts. Each subgroup effect will be estimated separately, one subgroup per model.

205  
206 Previous studies have suggested that race and/or eye color may interact with the  
207 treatment effect of atropine. Several studies have consistently found atropine to be  
208 effective in East Asian populations and a meta-analysis has suggested that atropine might  
209 be more effective in Asian populations than in white children, although this conclusion is  
210 limited by the lack of studies in non-Asian populations. Other research has shown that  
211 atropine is rapidly taken up by melanocytes and released over time, leading to a longer  
212 time to achieve mydriasis and a prolonged mydriatic effect in heavily-pigmented eyes as  
213 atropine is released over time, potentially leading to an increased treatment effect.  
214 Conversely, if the mechanism by which atropine slows myopic progression is through  
215 local retinal effects, one might speculate that higher melanocyte density might prevent  
216 the atropine from reaching the retina, which might result in brown eyes having less  
217 treatment effect than non-brown eyes.

218  
219 Atropine might be expected to be more effective in children with lower amounts of  
220 myopia given more potential for suppression of myopia progression. Likewise, atropine  
221 might be hypothesized to have a greater treatment effect in younger than in older children  
222 given they are earlier in the course of myopic progression and have more room for  
223 potential suppression.

224  
225 For each time point, the planned subgroup analyses also will be conducted using a  
226 continuous time longitudinal model, if linearity assumptions with time are met, to obtain  
227 p-values for the subgroup effect. Even if change in SER is not precisely linear with time,  
228 if it is monotonically decreasing, the continuous model is expected to have higher power  
229 than the discrete time primary analysis model, and will be favored over the discrete time  
230 model for obtaining p-values. The baseline factor and the baseline factor by treatment  
231 interaction will be included as terms in the model, and the 3-way subgroup, time, and  
232 treatment interaction will be used to determine whether there is a significant subgroup  
233 effect. The false discovery rate for the subgroup analyses will be controlled using the  
234 two-stage step up FDR procedure to control the overall FDR at 5%. Subgroup analyses  
235 will be interpreted with caution, particularly if the corresponding overall analysis does  
236 not demonstrate a significant treatment group difference.

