44 and treatment group and adjust for baseline SER, age, iris color (brown vs. non-brown),  
45 and race (East Asian vs. non-East Asian), to account for potential residual confounding,  
46 and improve power for the treatment comparison. The web data entry system mandated  
47 that baseline SER, age, and iris color could not be missing at enrollment. The value  
48 ‘unknown’ will be used in the mixed model for missing race/ethnicity value.

49  
50 Given that at most a small number of participants of East Asian race are expected to have  
51 non-brown iris, there is a possibility of partial aliasing when including both race and iris  
52 color in the mixed model. If the fully-adjusted model fails to converge, or displays  
53 evidence of estimate instability, such as very large standard error associated with a  
54 partially-aliased covariate, the race and iris color variables will be combined as follows:  
55 East Asian (regardless of eye color), non-East Asian with brown eyes, non-East Asian  
56 with non-brown eyes. The number of East Asians with non-brown eye color will be  
57 tabulated and reported.

58  
59 At baseline and all follow-up visits, including the 24-month visit, the mean of the three  
60 readings from autorefraction in each eye will be calculated and the mean of both eyes for  
61 each participant will be used for the analysis. If fewer than 3 readings are available in  
62 each eye, the mean of available readings will be used for each eye to obtain the mean of  
63 both eyes for each participant. If data from only one eye is available, the mean of  
64 readings on that eye will be used for analysis.

66 The mean change from baseline to 24 months in SER in each treatment group and the  
67 treatment group difference (atropine – placebo), together with their corresponding 95%  
68 confidence intervals, will be estimated using the mixed model with maximum likelihood  
69 estimation. Maximum likelihood estimation gives unbiased estimates of treatment effect  
70 in the presence of missing outcome data, as long as the missing data is missing at random  
71 (MAR) conditional on the variables included in the analysis model. The 2-sided null  
72 hypothesis of mean treatment difference equals zero (superiority hypothesis) will be  
73 tested at an alpha level of 0.05.

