## 142 **3. Secondary Outcomes**

143 The overall false discovery rate (FDR) in the secondary analyses specified in Section 3  
144 below will be controlled at the 5% level using the two-stage step-up false discovery rate  
145 procedure of Benjamini, Krieger, and Yekutieli. This involves first applying the false  
146 discovery rate procedure of Benjamini and Hochberg at alpha level = (overall  $\alpha$ )/(overall  
147  $\alpha + 1$ ) to estimate the number of true null hypotheses, and then applying the adaptive  
148 FDR adjustment conditional on the number of true null hypotheses. This method  
149 generally has better power than the usual Benjamini-Hochberg FDR method.  
150  
151

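### SAP Section 3.1 tests the progression proportions without covariates, unlike every other efficacy comparison, and gives no reason; adjusting would be a cheap, minor gain

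*SAP*

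**What the plan says.** SAP Section 3.1 sets three progression thresholds (0.5, 1 and 2 D). The proportions from baseline "to 12, 24, and 30 months in each treatment group will be tabulated", and they will then "be compared between treatment groups using Barnard's test". That is 3 × 3 = 9 comparisons. No covariate, effect estimate or confidence interval is named. The p-values fall under the Section 3 multiplicity rule, by which the false discovery rate "below will be controlled at the 5% level using the two-stage step-up false discovery rate" procedure.

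The other efficacy comparisons are adjusted:

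- **Section 1, primary SER model:** baseline SER, age, iris color and race. The stated purpose is to deal with residual confounding "and improve power for the treatment comparison".
- **Sections 1.2 and 2:** the same covariates in the ANCOVA sensitivity analysis and at 30 months.
- **Sections 3.2 to 3.4:** the primary covariates or the primary model, for axial length and for 12-month SER. Section 3.2 also asks for a group difference with a 95% interval.
- **Section 3.5, post hoc:** age, iris color and race, with baseline accommodation in place of baseline SER.
- **Sections 4, 5.1 and 5.2:** built on the primary model or using its covariates.

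The remaining unadjusted tests, in Sections 6.1 and 6.2, are safety analyses.

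**The concern.** The endpoints in Section 3.1 are cut-points of the same SER change that Section 1 analyses with adjustment, in the same children and with the same baseline data. Section 1 says that baseline SER, age and iris color cannot be missing, and it gives unknown race its own level. The data needed for adjustment are therefore already in hand.

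The revision history for SAP version 2.1 explains why the time-to-progression model was dropped: too many interim visits were missed because of COVID. That is a reason to leave a time-to-event analysis. It is not a reason to leave covariates out, because a logistic model fitted at one visit needs no interim visits.

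Two things are at stake. If the covariates are prognostic, the unadjusted comparison is less precise than the data allow. A chance imbalance in age or baseline SER between the 2:1 arms can also shift the progression result while the SER result is adjusted for it, so two summaries of one measurement could differ for that reason alone.

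**Working it through.** **The plan's own figure.** There is none to reproduce. The SAP states no sample size, progression rates, power or covariate strength. From the SAP come the 2:1 allocation, the nine cells, the four covariates and the two-sided 0.05 level of the primary test, used here per comparison before the false discovery step. Everything else is assumed: N of 180 or 300; 44% (placebo) versus 29% (atropine) with at least 1 D progression; covariates explaining 10%, 20% or 30% of the variance of SER change (R²).

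**Step 1: unadjusted power, N = 180 (120 and 60).** This uses the pooled z statistic, which also orders the tables in the form of Barnard's test that was simulated.

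- Difference D = 0.44 − 0.29 = 0.15
- Pooled proportion = (120 × 0.29 + 60 × 0.44)/180 = 61.2/180 = 0.34
- SE under the null = √[0.34 × 0.66 × (1/120 + 1/60)] = 0.0749
- SE under the alternative = √[0.29 × 0.71/120 + 0.44 × 0.56/60] = 0.0763
- Power = Φ[(0.15 − 1.96 × 0.0749)/0.0763] = Φ(0.042) = 52%

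**Step 2: adjusted power.** In simulation (4,000 replicates per setting), the ratio r of unadjusted to adjusted variance of the risk difference was 1.05–1.06, 1.12–1.14 and 1.21–1.23 at R² of 0.1, 0.2 and 0.3. Since 1 − 1/r is the reduction, the adjusted variance is about 5–6%, 11–12% and 17–19% smaller. Dividing both standard errors by √r gives power = Φ[(0.15√r − 1.96 × SE null)/SE alternative]. For N = 300 the standard errors are 0.0580 and 0.0591.

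| R² | N = 180: unadjusted → adjusted | N = 300: unadjusted → adjusted |
|---|---|---|
| 0.1 | 52% → 54% | 73% → 75% |
| 0.2 | 52% → 56–57% | 73% → 78% |
| 0.3 | 52% → 59–60% | 73% → 81% |

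The gains are about 2, 5 and 8 points.

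**Step 3: comparison with direct simulation of the logistic score test.**

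- N = 180: 52 → 55%, 52 → 58% and 52 → 60% at the three R² values.
- N = 300: 70 → 72%, 69 → 74% and 70 → 78%.
- N = 190: 52 → 53%, 52 → 57% and 51 → 59%.

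The simulation error of one estimate from 4,000 replicates is about √(0.25/4000) = 0.8 points, so the one-point gain at N = 190 and R² 0.1 cannot be told from zero or from two.

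**Step 4: other event rates, N = 180, R² 0.1, 0.2 and 0.3.**

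- 70% versus 50%, score test: 73 → 76%, 75 → 80%, 73 → 81%.
- 20% versus 8%, score test: 65 → 66%, 64 → 66%, 64 → 70%.
- 5% versus 1%, exact Barnard's test against a logistic likelihood-ratio test: 41 → 41%, 41 → 44%, 42 → 44%. Logistic coefficients diverged in 67–75% of these data sets.

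**Step 5: type I error, N = 180, R² of 0 and 0.2.** The score test rejected 4.4–5.7% of the time at event rates from 3% to 60%. Further runs at other sample sizes gave up to 6.6%. The exact Barnard's test rejected 3.6–5.1% of the time. The logistic likelihood-ratio test rejected 6.3–6.7% at a 10% event rate and 8.2–9.3% at 3%.

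**The case against.** A reader might infer that Section 3.1 is wrong, or that power is given away for nothing. The document does not support either. An unadjusted exact test is valid under randomisation without a model. It keeps its level in sparse cells, such as perhaps 2 D at 12 months, where logistic coefficients often diverge. Section 1 gives its reasons for adjustment for the primary SER model and sets no rule for binary outcomes, so there is no contradiction. Chance imbalance is part of the sampling variation that the test's level already covers.

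The stakes are also limited. SER change is tested with adjustment at 12, 24 and 30 months, the same three times, and the efficacy conclusion does not hang on the dichotomised version.

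It is tempting to cite Section 4 as the SAP's own evidence that age predicts progression, since it describes younger children as "given they are earlier in the course of myopic progression and have more room for" suppression. That sentence supports a hypothesis about a larger treatment effect in younger children. It concerns effect modification and says nothing about how strongly age predicts crossing a threshold. Nothing in the SAP supports an R² of 0.2 to 0.3, and at 0.1 the gain is small.

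All of this stands, and it sets the severity. Two parts of the case against adjusting do not carry through. The inflated type I error of 8–9% belongs to the likelihood-ratio test, not to the score test. The sparse-cell problem is met by keeping Barnard's test there. What remains is that the SAP gives no reason for leaving the covariates out.

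**Conclusion.** The point holds as a minor suggestion. Section 3.1 is the only efficacy comparison that uses no baseline covariate, and the SAP does not explain it. Barnard's test is valid, so nothing has to be corrected for the analysis to be sound.

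Under the assumed inputs (N 180 to 300, 2:1, 44% versus 29%), adjustment adds about 2 to 3 points of power at R² 0.1 and about 4 to 9 points at R² 0.2 to 0.3. It adds less for rarer events. None of these inputs comes from the SAP. If the covariates barely predict progression, the gain is close to nil.

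**What to change.** In SAP Section 3.1:

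1. Fix, before analysis, a minimum number of events over both arms combined that decides which test a cell receives.
2. Where it is met, compare the proportions with a logistic model containing treatment, baseline SER, age, iris color and race. If the model is unstable, use the combined race and iris variable from Section 1, and state where participants of unknown race go in it, since Section 1 does not. In one simulation with an assumed 2% of unknown race, a coefficient diverged in about 40% of data sets even for the 1 D threshold.
3. Take the p-value from the score test. Report the standardised risk difference with a 95% confidence interval, naming the delta method or the bootstrap. This also supplies the effect estimate that Section 3.1 lacks.
4. Keep Barnard's test for the sparser cells.
5. Enter one pre-specified p-value per cell into the Section 3 false discovery procedure.

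The cost is a short paragraph of SAP text and standard software. The downside is that the adjusted test is not exact (size roughly 5 to 6%) and that a sparse-cell rule has to be set and followed.

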
VERSION NUMBER		AUTHOR	APPROVER	EFFECTIVE DATE	REVISION DESCRIPTION (INCLUDING SECTIONS REVISED)
SAP	Protocol				
					
problem in the analyses of results of interim visits when using Barnard's test, the 24-month primary time point is largely unaffected, as the amount of missing data is minimal.
 
3.Per discussion with the study leads, to evaluate biologic activity of the drops, and the potential effect of dilute atropine on accommodation, as a post hoc analysis, mean binocular near point of accommodation at 6 months was compared between treatment groups using an ANCOVA model, adjusting for baseline binocular near point of accommodation, age, iris color (brown vs. not brown), and race (East Asian vs. non-East Asian).

20

21 The primary objective of MTS1 is to determine the efficacy of daily low-dose atropine  
22 (0.01%) for slowing myopia progression over a two-year treatment period in children  
23 aged 5 to less than 13 years with myopia -1.00D to -6.00D at the time of enrollment.

24  
25 Participants are randomly assigned 2:1 to the following two treatment groups:

- 26 • Atropine Group: 0.01% atropine eyedrops administered 1 drop to each eye daily for  
27 24 months, followed by 6 months off atropine eyedrops
- 28 • Placebo Group: Placebo eyedrops administered 1 drop to each eye daily for 24  
29 months, followed by 6 months off placebo eyedrops

30  
31  
32 **1. Primary Analysis: Refractive Error at 24 Months (On-Treatment)**

33 The primary analysis will be a treatment group comparison of mean change from baseline  
34 to 24 months in spherical equivalent refractive error (SER), as measured by a masked  
35 examiner using cycloplegic autorefraction, using a longitudinal discrete time mixed  
36 model. The population-averaged method will be used to model the repeated measures on  
37 SER at 6, 12, 18, and 24-month visit. The time variable will be categorical to not impose  
38 assumptions regarding trend of SER over time. The correlations between SER  
39 measurements within person across visits will be estimated and a correlation structure  
40 will be selected accordingly. (Given that the follow-up visits are approximately equally  
41 spaced, an autoregressive covariance structure is considered likely. Other correlation  
42 structures will also be fitted, and the information criteria will be used to select the most  
43 appropriate covariance structure.) The model will include the interaction between time  

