### 243 244 **5.1. Treatment Effect Over First Year of Treatment**

245 The treatment effect on change in SER from baseline through the first year will be  
246 compared with the treatment effect on change in SER from end of first year through the  
247 second year, by constructing the appropriate contrasts in the primary analysis model.

249 **5.2.Exploratory Analyses of Additional Ocular Biometric Parameters**

250 As exploratory analyses at 24 and 30 months, change in flat corneal radius, anterior  
251 chamber depth, and lens thickness from baseline will each be compared between  
252 treatment groups using a longitudinal discrete time mixed model with maximum  
253 likelihood estimation, including the interaction between time and treatment group, and  
254 adjusting for the baseline covariates from the primary analysis model. The same  
255 strategies specified in the primary analysis (Section 1, excluding sensitivity analysis) will  
256 be used to choose the appropriate covariance structure for the model.

257  
258 At baseline and all follow-up visits, including the 12 and 24-month visits, the mean of the  
259 readings in both eyes for each participant will be used for the analysis. If data from only  
260 one eye is available, the reading on that eye will be used for analysis. The treatment  
261 group differences (atropine – placebo) and a 95% confidence interval will be estimated  
262 using the mixed model.

263  
264 **5.3.Data Tabulations**

265 The following tabulations will be performed both according to treatment group and  
266 among overall sample:

- 267 • Baseline demographics and clinical characteristics
- 268 • A flow chart accounting for all participants for all visits and phone calls
- 269 • Visit and phone contact completion rates for each follow-up visit
- 270 • Protocol deviations
- 271 • Proportion of participants needing bifocals by 24 months (i.e. during treatment)

272  
273 **5.4.Compliance**

274 Compliance with study medication will be assessed at the 6-month, 12-month, 18-month,  
275 and 24-month outcome exams. For each of these exams, the proportion of calendar days  
276 that study medication was reported used and the proportion of unused study medication  
277 ampules will be tabulated in each of the two treatment groups.

278  
279 Compliance with refractive correction will be assessed at the 6-month, 12-month, 18-  
280 month, and 24-month outcome exams. After discussion with the parent and child, study  

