**7. Interim Monitoring**

By the time sufficient data allowing for an analysis of efficacy or futility for the primary outcome would be possible, all or most subjects are expected to be within 1 year of completing the primary outcome; hence, no formal statistical interim monitoring is proposed.

Tabulated safety and efficacy data will be reviewed by the PEDIG Data and Safety Monitoring Committee (DSMC) at its biannual meetings, and if any unexpected safety or other issues arise, they can recommend stopping the study at any time.

During the DSMC meeting in October 2019, the DSMC approved the proposal of NOT performing interim monitoring analysis for futility based on the rationale that by the time 50% of the 24-month data are available (May 2021), the recruitment will have been finished and the remaining participants will have between <1 to 7 months of remaining time on treatment before all participants have 24-month data (December 2021). The DSMC also approved the proposal of NOT performing interim monitoring analysis for efficacy based on the rationale that even if efficacy was found in an interim analysis for the 24-month on-treatment primary outcome analysis, the 30-month off-treatment secondary analysis is needed to understand whether the benefit persists after treatment is discontinued.

328 **References**

329

330 1. Benjamini Y, Krieger AM, Yekutieli D. Adaptive linear step-up procedures that control  
331 the false discovery rate. *Biometrika*. 2006;93(3):491-507.

332 2. SAS Institute Inc. SAS/STAT® 14.3 User's Guide 2017. In: Cary, NC: SAS Institute  
333 Inc:6564-6567.

334 3. Benjamini Y, Hochberg Y. Controlling the False Discovery Rate: A Practical and  
335 Powerful Approach to Multiple Testing. *Journal of the Royal Statistical Society Series B*  
336 *(Methodological)*. 1995;57(1):289-300.

337 4. Benjamini Y, Hochberg Y. On the Adaptive Control of the False Discovery Rate in  
338 Multiple Testing With Independent Statistics. *Journal of Educational and Behavioral Statistics*.  
339 2000;25(1):60-83.

340 5. Newman SC. Commonalities in the classical, collapsibility and counterfactual concepts  
341 of confounding. *Journal of clinical epidemiology*. 2004;57(4):325-329.

342

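### The axial length and biometric models adjust for baseline SER but not for the baseline value of the outcome being analysed (SAP Sections 3.2, 3.3 and 5.2)

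*SAP*

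**What the plan says.** - **Section 1** sets the primary covariates. The model is to include the time by "treatment group and adjust for baseline SER, age, iris color (brown vs. non-brown") and race, and the list ends there. One stated purpose is to account for residual confounding; the other is to adjust "and improve power for the treatment comparison". The modelled responses are the follow-up visits only, so baseline enters as a covariate and not as a response.
- **Section 3.2** compares change in axial length at 12 and 24 months with a model that allows for the time by treatment interaction "and adjusts for the same baseline covariates as the primary analysis".
- **Section 3.3** covers axial length at 30 months and lists no covariates. It says: "The same approach defined in Section 3.4 will be used to conduct a treatment group" comparison. Section 3.4 is the 12-month SER analysis, which refers back to Section 1. The axial length method is in Section 3.2.
- **Section 5.2** models change in corneal radius, anterior chamber depth and lens thickness, "adjusting for the baseline covariates from the primary analysis model".
- **Section 3.5**, by contrast, names the baseline of its own outcome (near point of accommodation) alongside age, iris color and race.

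**The concern.** In the primary model, baseline SER is the baseline of the outcome. Copied unchanged to other outcomes, the list keeps baseline SER and drops that role. The models in Sections 3.2 and 5.2, and in 3.3 by reference, therefore analyse change without adjusting for the value from which the change is measured.

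Two things are at stake. Any variance in the change that is explained by the outcome's own baseline, and not already by the listed covariates, stays in the error term. And a chance difference between arms in that baseline carries into the estimate. Baseline SER protects against this only as far as it correlates with the outcome's baseline. The Section 3 tests belong to a family with false discovery rate control, so precision lost there can affect which results are declared.

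The reference in Section 3.3 adds a practical problem: a covariate added in 3.2 alone would not reach the 30-month axial length model.

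**Working it through.** The SAP gives no SD, correlation or power figure for these outcomes, so there is no plan figure to reproduce. All inputs below are assumptions, except the 2:1 allocation: "Participants are randomly assigned 2:1 to the following two treatment groups".

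**1. One visit, common baseline slope in both arms.** Let the outcome's baseline X have SD 1, the follow-up Y have SD k, and corr(X, Y) = rho. Let baseline SER have correlation c with X and act on Y only through X. Age, iris color and race are left out.

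- Residual variance of change with SER only (as written): 1 + k² − 2·rho·k − c²(1 − rho·k)²
- Residual variance with X added: k²(1 − rho²)

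Ratio of the second to the first, at k = 1:

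| rho | c = 0 | c = 0.5 | c = 0.8 |
|---|---|---|---|
| 0.98 | 0.990 | 0.9925 | 0.9964 |
| 0.95 | 0.975 | 0.9811 | 0.9909 |
| 0.90 | 0.950 | 0.9620 | 0.9814 |
| 0.80 | 0.900 | 0.9231 | 0.9615 |

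Example: at rho = 0.80, c = 0.5, the ratio is 0.36 / (0.40 − 0.25 × 0.04) = 0.36 / 0.39 = 0.9231.

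Over k from 0.95 to 1.10 the reduction runs from about 0% to 15%. At k = 1.05, rho = 0.95 there is none, because rho·k is about 1. At the corner k = 0.95, rho = 0.80, c = 0 the ratio is 0.3249 / 0.3825 = 0.849.

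**2. In terms of power.** If the model with X had 80% power, the model as written has Φ(2.802·√ratio − 1.960). At k = 1, c = 0 this is 78.0% for rho = 0.90 and 79.6% for rho = 0.98.

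**3. Chance imbalance.** With c = 0, a baseline difference d between arms shifts the unadjusted contrast by (k·rho − 1)·d. That is −0.10·d at rho = 0.90, k = 1.

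**4. Two-visit mixed model (12 and 24 months).** Simulation with maximum likelihood, unstructured covariance, assumed n = 180 at 2:1, residual correlation 0.7, k = 1, c = 0.5, a common slope across arms, and 2,000 runs. Ratio of 24-month variances with X by visit added:

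| rho at 12 / 24 months | Complete data | 30% / 5% missing |
|---|---|---|
| 0.98 / 0.95 | 0.977 | 0.976 |
| 0.95 / 0.90 | 0.953 | 0.953 |
| 0.90 / 0.80 | 0.906 | 0.906 |

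Monte Carlo SE is 0.007 to 0.013. With a single slope for both visits and complete data, the ratios are 0.983, 0.963 and 0.931, so the interaction with visit does some work. Where the true gain is zero (k 1.02/1.05, rho 0.98/0.9524), the ratio is 1.011 with complete data and 1.009 with missing data.

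**5. Slopes that differ by arm.** Section 4 raises the possibility that the effect on SER varies with baseline: "Atropine might be expected to be more effective in children with lower amounts of" myopia. Let b1 (atropine) and b0 (placebo) be the slopes of change on X, with 2:1 allocation, residual SD 0.3 and b = (2·b1 + b0)/3.

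- n × Var(unadjusted) = 1.5(b1² + 0.09) + 3(b0² + 0.09)
- n × [Var(unadjusted) − Var(adjusted by a main effect)] = 4.5·b·b0

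The difference is negative only if b1 and b0 have opposite signs and |b1| > |b0|/2.

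| b1 / b0 | Adjusted / unadjusted | Ratio | Simulated, n = 180 |
|---|---|---|---|
| 0.10 / −0.05 | 0.43875 / 0.4275 | 1.026 | 1.033 |
| −0.20 / 0.05 | 0.49875 / 0.4725 | 1.056 | 1.073 |
| −0.10 / −0.05 | 0.40875 / 0.4275 | 0.956 | 0.962 |
| −0.10 / −0.10 | 0.405 / 0.450 | 0.900 | 0.909 |

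**The case against.** The strongest reply is that nothing here is invalid. A prespecified, covariate-adjusted model of change is unbiased under randomization, the power claim in Section 1 is made for the SER model, and the gain may be nil or negative. At a correlation of 0.9 or more with equal SDs, about 2 points of power at most are at issue. The calculation also leaves out age, iris color and race, whose effect on the gain could go either way. All of this stands, and it limits the point to a minor one.

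The cost side must also be read in full: at n = 180 the worst simulated slope case gives a variance increase of 7.3%, above the 5.6% from the large-sample formula. The remark in Section 4 is tentative and concerns SER, so it shows only that unequal slopes are conceivable.

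It can also be argued that the same approach in Section 3.3 means, by analogy, the baseline of axial length. The wording of 3.3 leaves room for that. The wording of 3.2 and 5.2 does not, since both refer to the primary covariates themselves. Section 3.5 suggests that the outcome's own baseline is named when it is meant, although that analysis is post hoc and compares a 6-month mean. If the analogy was intended, the text still needs to say so, because two programmers could build different models.

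**Conclusion.** The point holds and is minor. Read as written, the models in Sections 3.2 and 5.2 omit the baseline of the outcome analysed. So does the model in 3.3, if Section 1's covariate list is taken literally, and its cross-reference points to the wrong section in any case.

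The size is unknown and probably small. With k = 1, a common slope, rho 0.80 to 0.98 and c 0 to 0.8, variance would fall by 0.4% to 10%; across k 0.95 to 1.10 the range is about 0% to 15%. The reading of the text is firm. The figures rest wholly on assumed correlations, SD ratios and slopes. The comparisons remain unbiased and the primary SER analysis is untouched.

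**What to change.** 1. In Section 3.2, keep the existing covariates and add baseline axial length, interacted with visit because its slope may differ by visit.
2. In Section 5.2, add the baseline value of each parameter in the same way.
3. In Section 3.3, refer to Section 3.2 instead of 3.4, so that the change reaches the 30-month model.

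This takes one phrase in each of two sections and one corrected reference. The data are already collected. Each model spends one degree of freedom per visit. The price is about 1% in variance where the true gain is zero, and a few percent (up to 7.3% in the cases simulated) if slopes have opposite signs by arm.

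Timing matters. Version 2.1 is dated November 28, 2022, while Section 7 speaks of the time remaining "before all participants have 24-month data (December 2021"). If these outcomes have already been analysed, keep the planned model as the reported analysis and add the baseline-adjusted model as a labelled supplementary analysis.
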